### **Fitness Testing Appointment:**

The total time for the fitness testing will be around 45 minutes, and each of the tests will measure a part of fitness. This will occur on UNH campus in NH hall or in the firehouse if for convenience the crew would like to meet at the firehouse. We only allow this if the firehouse has a treadmill. This is also allowed since for the safety of the community protected by the fire crew, we need to keep them close to the firehouse in case a 911 call comes in, then they are able to immediately respond. Also, past cohorts of this study have been offered this so to keep the study consistent, this policy will continue. A seated clinical blood pressure measurement will be taken first. The fitness test session includes: plank pose, stairway climb, 12-step climb, right and left single-leg stand, wall sit, and a treadmill test. All tests will be done in civilian fitness clothing.

Plank pose test to assess core strength. Hold plank position until exhaustion or when the position is compromised. Data will include total time.

Stairway climb test to assess leg endurance/strength. Climb up/down stairs for 2 minutes. Data will include total number of steps.

12-step climb test to assess agility and power. Ascend 12 steps as fast as possible. Data will include total time.

Balance test. Stand on single leg while holding a 15 lb dumbbell until exhaustion or balance is lost. This will be repeated with the other leg. Data will include total time.

Wall sit test to assess functional ability and leg strength. Squat down to sitting position with back flat against the wall, legs at 90-degree angle, and knees over the heels. Hold until exhaustion or when position is compromised. Data will include total time.

Aerobic fitness will be measured by an estimated calculation of  $VO_{2\text{peak}}$ . The protocol used is the **Wellness Fitness Initiative** protocol, which is a submaximal treadmill test established for firefighters. This protocol is based on the NFPA 1582 *Standard on Medical Requirements for Firefighters and Information for Fire Department Physicians* and the NFPA 1583 *Standard on Health-Related Fitness Programs for Firefighters*. This submaximal test includes minute stages that take the participant to a target heart rate that is calculated based on age. The submaximal heart rate is less than 85% of the age-predicted maximal heart rate, which falls into the ACSM guideline classification for submaximal exercise test. We have found that in the prior cohorts of this study that test time varies between 2 and 20 minutes, depending on fitness of the participant. None of the participants reached 84% of their age-predicted max heart rate during the test, so it remains a submaximal protocol.

Functional strength test. This is a dummy drag (drag a rescue dummy for distance in 30 seconds) which is completed by the firefighters in the study. The civilian population will not complete this test.

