## [name] 2020 PROJECT OUTLINE: IRB #8242

### INTRODUCTION

Global hypertension rates have reached epidemic proportions with upwards of one billion individuals diagnosed and estimates that 1/3 of the global adult population is hypertensive. Blood pressure (BP) is a primary risk factor for cardiovascular disease. There are over a million firefighters in America, and firefighting is one of the most hazardous and dangerous jobs with an inherent increased risk of death, just by nature of the work. In fact, many firefighters have hypertension, and cardiac-related incidents are the leading cause of death among firefighters. Also, BP control remains an issue in firefighters, with close to 74% of hypertensive firefighters not having adequate control of their BP. Research that examines BP in firefighters is scarce, and quantifying the BP surge that occurs with pager activation has never been done.

It is known that exercise training improves cardiovascular health, lowers lipid levels, reduces inflammation, and reduces BP. Yet, it is interesting that the National Fire Protection Agency (NFPA) does not require fire companies to have fitness testing or programming for the crew. The NFPA has established that the demands of firefighting require a fitness level of a  $VO_{2\text{max}}$  equivalent of 42 ml/kg/min. Yet, only 20% of volunteer firefighters meet this fitness threshold. And, even worse is that <30% of fire stations have a fitness program or fitness monitoring as part of their standard operating procedures.

It is also known that a healthy diet improves cardiovascular health, lowers lipid levels, reduces inflammation, and reduces BP. Evidence suggests that the Mediterranean diet can improve cardiovascular health, and the Mediterranean diet has been touted the top heart-healthy diet for 2 years in a row. The diet includes a high consumption of fruits and vegetables, a moderate consumption of fish, nuts, low-fat diary, and wine, and a low consumption of red meat and other meat products. Dietary patterns like this reduce inflammation and improve vascular function, which will benefit firefighters. Firefighters know that diet is important, yet they don't know how to modify their diet. Importantly, a recent survey study done at Harvard found that the Mediterranean diet is one that firefighters actually would prefer.

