## **RESEARCH PROTOCOL**

This study is a pre-post exercise and diet intervention study with 2 groups: firefighters and civilians. For the study, firefighters will be recruited from local fire departments and civilians will be recruited from the surrounding areas. The only compensation will be for parking while they are on campus for testing appointments. A study description document is attached which will be used to supplement the word-of-mouth advertising done by walking into local firehouses.

The population is seemingly healthy and low-risk, so physician referral or approval is not needed. Criteria for inclusion: adult 18 years of age and older; no history of renal disease, diabetes, or cardiovascular incident requiring surgery; no existing orthopedic issues that preclude exercise; no more than one anti-hypertensive or cholesterol medication.

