#### ***Fasted Testing Appointment:***

The total time for this visit will be around 45 minutes. ***This test will occur on UNH campus in NH Hall.*** They will be required to fast for 10 hours before coming into the lab for the testing. For this visit, we ask that they avoid food or drink (water is allowed) for at least 10 hours before coming into the lab. We also ask that they avoid alcohol and exercise the night before. Height, weight, and blood pressure will be taken. Body composition will be measured, glucose and cholesterol levels measured, a blood draw collected, and blood vessel ultrasound and pressure studies will be done.

***Considering that the population is seemingly healthy based on other exclusion criteria, it is still possible to identify high blood pressure or high lipid/glucose levels in the participants. This would not be an exclusion from the study. If this occurs, we inform them and offer to provide them with the data, if they wanted to follow-up with their physician.***

**Body composition test** will tell the investigators what percentage of the body is fat, muscle and bone. The instrument that measures body composition is called bioelectrical impedance (BIA). The machine will cause a very small current to travel through the body for 2-3 seconds, but nothing will be felt. To do this test, they will lie on a table on their back with left foot exposed. To collect the measurements, a technician will place two electrodes on the left foot and two electrodes on left hand.

**Blood glucose and cholesterol measurements** will tell the investigators what the levels of fasted plasma glucose and cholesterol are. We will be measuring these with a finger-prick test. Only one finger prick will occur, and a single large drop of blood will be collected.

**Plasma inflammation, oxidative stress, and vasodilation levels.** A blood draw will occur where we collect 2 tubes of blood (equivalent of 7 tsp or 1.2 oz). This will allow us to measure common markers that circulate in the blood which are related to heart health.

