## RISKS

The possible **risks**, exactly as described in the consent form, include the following:

*Loss of Confidentiality:* Once others know that you are participating in the study, you may lose some confidentiality. Fire crews work in close quarters and some spend time living together in the fire house, so confidentiality may be lost by your presence at the testing appointments. We will reduce this risk because your name will not be on any documents and your personal data will not be shown to anyone during the test sessions.

*Depression, Anxiety, and Stress Scales (DASS-21):* The risk associated with completing this short 21-item survey is that you may feel uncomfortable while answering the questions. If you feel this and your symptoms are severe, we will work with you to refer you to a proper clinician who is part of your health network.

*Blood glucose, cholesterol, and blood draw:* These measurements will involve a finger prick and a needle stick. The risks associated are slight discomfort in the site. These are routine and conventional procedures used to measure blood levels of metabolites. Minor risks include a small amount of bleeding under the skin (bruising), but this has been reported in <10% of the cases, dizziness, and a very small risk of infection (1 in 1000). The risk of infection will be reduced by proper cleaning and antiseptic techniques by the technician.

*Blood vessel studies:* The blood vessel ultrasound studies may include discomfort in the arm and leg when the cuff squeezes to take a measurement. This feeling could be similar to what is felt when a foot or leg falls asleep after sitting in certain positions. This is not a risk to your health, but it is a discomfort. To help with this risk, we recommend that you stay very still and as the blood flows back to the arm and the feeling will go away.

*Fitness testing/training:* The risk of any exercise is injury to muscles, joints, ligaments, and tendons. It has been found that in 1 out of every 70,000 exercise tests, a person could die from heart problems. In medical terms, doctors call this a rare event. Because you are otherwise healthy with no known risk factors, the risks of a medical problem are even lower. You are aware that if any exercise makes you uncomfortable, you should notify us immediately.

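### In the available text no resting blood pressure, however high, defers the fitness session or the circuits; separately, one consent sentence is untrue for participants admitted on medication

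*Combined protocol and SAP*

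**What the plan says.** Fitness Testing Appointment: "A seated clinical blood pressure measurement will be taken first". The section then lists the plank, stairway climb, 12-step climb, single-leg stand, wall sit and treadmill test. It gives no BP value and no instruction to repeat, defer or refer.

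Fasted Testing Appointment: the plan expects that some participants will have high BP, lipids or glucose, and states its rule: "This would not be an exclusion from the study. If this occurs, we inform them and offer to provide them with the data". Seeing a physician is left to the participant.

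Research Protocol: "The population is seemingly healthy and low-risk, so physician referral or approval is not needed". The entry criteria set no BP ceiling and allow "no more than one anti-hypertensive or cholesterol medication".

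Risks, which the protocol presents as the exact consent wording: "Because you are otherwise healthy with no known risk factors, the risks of a medical problem are even lower".

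Introduction: "Blood pressure (BP) is a primary risk factor for cardiovascular disease".

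**The concern.** A resting BP is taken just before exertion, in a study whose own rationale is cardiovascular risk in firefighters, yet no value of it changes what happens next. The rule for the fasted visit treats a slightly raised reading and a very high one alike: the participant is told, and carries on. At stake is the safety of the few people at the top of the BP range, both in the session itself and in six weeks of exercise away from the lab.

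The consent sentence is a second, independent matter. It lowers the stated risk on the ground that the participant has no known risk factor, while the entry criteria admit people who are being treated for one.

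**Working it through.** The plan states no figure on this point to reproduce. The check is to look at each place where a BP limit could stand, and then to follow one participant through.

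**Places where a limit could stand**

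- *Research Protocol (entry criteria):* no BP ceiling; physician approval waived.
- *Orientation and consent:* a health questionnaire; no rule based on BP.
- *Fasted Testing Appointment:* inform and offer the data; no upper limit, no delay.
- *Blood Pressure Monitoring appointment:* no action attached to the ambulatory readings.
- *Fitness Testing Appointment:* BP taken first; no action attached.
- *Treadmill test:* a target below 85% of age-predicted maximal heart rate. This limits heart rate, not BP, and covers the treadmill only.
- *Consent renewed at each lab visit:* the day's measures are explained and the participant is asked whether consent still stands; BP is not used.
- *Exercise Training Component:* all participants do the circuits; no BP condition.
- *Risks:* participants are asked to report discomfort; BP is not used.

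None of these turns a BP reading into a delay.

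**Following a participant with a very high resting BP**

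1. Entry: admitted, since there is no ceiling and no medical approval.
2. Fasted visit: told of the reading and offered the data; stays in.
3. Fitness visit: BP is read again and the tests proceed. The protocol fits appointments to the participant's schedule and lists the three baseline components in different orders in two places. The seated reading at this visit could therefore be the first one the study takes.
4. Circuits: start as scheduled at home, in the station or in a fitness center, with completion self-reported.

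**Extent per participant**

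- Fitness sessions: 1 before + 1 after = 2.
- Tests other than the treadmill: plank, stairway climb, 12-step climb, single-leg stand, wall sit = 5; with the firefighters' dummy drag, 5 + 1 = 6.
- Of these, holds continued to exhaustion or loss of position or balance: plank, single-leg stand, wall sit = 3.
- Circuit workouts: 3 per week × 6 weeks = 18, with one start.

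**Consent sentence**

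Consent is signed at orientation, before testing. For someone admitted on an anti-hypertensive or cholesterol drug, the treated condition is already known then. The Introduction calls BP a primary risk factor, and the Specific Aims count clinical BP and lipid levels among the measures of cardiovascular risk. The sentence is therefore untrue for that person at signing, assuming the drug is taken for its usual purpose. For someone whose high BP, lipids or glucose first appear at testing, the factor was not yet known at signing. There the sentence becomes wrong later, and nothing in the available text says that it is then corrected.

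**The case against.** **The rule is deliberate and disclosed.** The protocol foresees high BP, keeps such participants in, informs them, and gives its reason for waiving physician approval. This stands. A reader might infer that the plan has no response to a high BP at all; the fasted-visit rule shows otherwise. What remains is that the rule has no upper limit and delays nothing.

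**The seated reading may be outcome data.** The Specific Aims list clinical BP as a measure of cardiovascular risk, and nothing says that the fitness-visit reading was meant as a safety screen. A reader might infer a screen whose action was forgotten; the text does not support that. The reading is nevertheless available at the right moment.

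**Harm is not shown.** No section says that these tests are hazardous at high BP. The holds may end early on loss of position or balance, and the plank in the circuits is limited to 45 seconds. The consent text gives 1 death per 70,000 exercise tests. These points rule out any claim about the size of the risk. The 1 in 70,000 is a general figure, though, and is not given for people with very high BP.

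**Text not seen.** The part of the document between the post-intervention testing visits and the Data section was not available, nor was the named treadmill protocol. Either may contain a limit.

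**How many are affected.** It is tempting to combine "close to 74% of hypertensive firefighters not having adequate control of their BP" with an assumed prevalence of hypertension. That would count uncontrolled BP rather than very high BP, and would ignore this study's entry criteria. It does not size this point.

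**The consent error might seem to cover everyone with high BP.** It does not: at signing, it is established only for those admitted on such a drug.

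**Conclusion.** The point holds in two parts of different strength.

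First, in the available text no resting BP defers the fitness session or the start of the circuits, and the one stated rule keeps a participant in at any value. Adding a limit is a cheap safety improvement to a deliberate choice, not the repair of a contradiction. It concerns two fitness sessions and one start of the circuits per participant. The number of participants above any limit is unknown. The conclusion assumes that the unseen text contains no limit; for the treadmill test in particular that is open.

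Second, the consent sentence is wrong as written for participants admitted on an anti-hypertensive or cholesterol drug. This part stands without the first and does not support it.

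**What to change.** **BP limit**

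- Before enrolment, the investigator fixes on medical advice an upper resting value, clearly above the ordinary control level, so that the hypertensive firefighters who motivate the study are not excluded. No value is proposed here: the documents give none, and it is a medical decision.
- If the seated reading at the fitness visit is above the value, repeat it. If it is still above, defer the session and, at baseline, the start of the circuits, and refer the participant.
- Limit the fasted-visit rule, under which high BP is no exclusion, to values below this limit.
- At the post-test, reschedule rather than drop the participant, still collect the outcomes that need no exercise, and report any fitness tests missing because of the limit.

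**Consent**

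- Reword the sentence so that it does not tell every participant that no risk factor is known.
- Tell participants whose high BP, lipids or glucose are found at testing that the reassurance no longer applies to them. The renewal of consent at each lab visit is a natural place for this.

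**Cost**

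A short protocol and consent amendment, medical advice once, and no new scheduled measurement. A few participants at the top of the BP range would be deferred or lost. Referral may lead to new treatment during follow-up, which a pre-post study without an untreated arm cannot separate from the intervention. Some post-test fitness data may be missing in a way that depends on BP, itself an outcome; the paired and repeated-measures comparisons of fitness would then lean towards participants with lower BP. Rescheduling reduces this, and reporting makes it visible.

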### **6-Week Intervention: Mediterranean Diet Component**

#### **Pre-Intervention Diet Training:**

The total time for this training appointment will be around 45 minutes. We will issue a **study** training manual and teach the serving sizes for the food groups in the Mediterranean Diet. For the entire 6-week period, the diet will be followed.

Also, before starting the diet, each participant will write down all the food that is consumed for a 3-day period. This will give us a baseline assessment of how their diet is before they start the study, and this will guide us to the number of serving sizes to prescribe. We only collect 3-day diet once during the study in order to quantify basic caloric consumption.

#### **Diet Intervention:**

The Mediterranean diet includes a high consumption of fruits and vegetables, a moderate consumption of fish, nuts, and wine, and a low consumption of red meat and other meat products. Also, olive oil is the principal source of fat instead of other types of oils. We teach them these basics and the manual has many examples.

During the study, all participants will receive the diet information, will have online access to diet information by our website, <http://www.theheartlab.org/#dietexercise>, will receive weekly educational documents and tips through email, will be provided with informational websites, and receive many lessons on serving size. We also provide all participants with sample serving size containers to get them started.

For the duration of the diet intervention, they will be asked to track their diet and enter serving numbers into our research website each week. The manual and the website have a nice checklist that can be used to track their weekly diet.

Also, the **study** manual and website have been used for the prior cohorts of data collection for this study.

Here is a quick summary of the number of servings per week they will target and track during each week of the diet intervention (some serving numbers may be reduced based on body size though):

Vegetables = more than 28 per week  
Low/Non-Fat Dairy = 14-21 per week  
Fish = more than 4 per week  
Red Meat = less than 2 per week  
Nuts/Healthy Oils = less than 8 per week  
Sweets/Processed Food = less than 4 per week

Fruits = more than 21 per week  
Grains/Potatoes = 42-49 per week  
Poultry = less than 3 per week  
Beans = more than 3 per week  
Other Fats/Oils = less than 8 per week

## **6-Week Intervention: Exercise Training Component**

The exercise intervention will be self-report. This means that the exercises will be done at home or in the fire house or in a fitness center. All participants are asked to complete the circuit workout 3 times per week for the 6-week period. For the workout, each station below will be done 3 times within each workout, and it should take around 45 minutes. The workout can be done by going through each station and rotate back around 3 times, or the workout can be done by doing each station 3 times and moving on to the next station. Either way that they choose to complete the workout, the amount of work that they will do is the same, so it gives flexibility to pick each time.

### *Circuit Exercise Stations and Directions:*

1. Unsteady Carry – carry 40 lb or an extrication tool for 100 ft (50 ft over and back)
2. Stairway Run/Walk – ascend and descend a stairway continuously for 3-minutes
3. Plank Pose- hold plank pose for 45 seconds. If cannot hold for 45 seconds, hold for as long as possible.
4. Weighted Carry – carry 20 lb or a fireground tool for 100 ft (50 ft over and back), moving as fast as possible.
5. R/L Single Leg Stands – stand on single leg while holding a 15 lb dumbbell or fireground tool for as long as can maintain balance. Repeat with other leg.
6. Stairway Carry – carry 15 lb dumbbell or fireground tool up and down the equivalent of 30 steps.

## **Post-Intervention Testing Visits**

They will complete the exact same tests after the intervention as they did before.

## **DATA**

Data will be deidentified in study database and when shared with the sponsor. All participants will be assigned an ID code upon entry into the study. All data collection forms will have this ID number listed, with no identifying information at all on the data sheets. We will keep all documentation safely locked in a locked office, in a locked file cabinet. All data points will be entered based on the ID number, and all data will be stored on UNH Box. Only the PI and students affiliated with the study will have access to the data and any data kept on Box will be deidentified.

Data will be aggregated and presented in publications and presentations.

The only form with identifying information will be the Health History form. Upon study completion, any identifying information will be destroyed by shredder. As the study is sponsored by the American Heart Association, the approved data plan states that data will be made available through clinicaltrials.gov.

Our interest is in estimating the effect of exercise and diet on the change in blood pressure surge and examine whether it differs between groups. Quantitative analysis will be done. Data will be expressed as mean  $\pm$  the standard deviation, and statistical analyses will be performed using SPSS. The distribution of all variables will be examined using the Shapiro-Wilk test of normality. Repeated measures ANOVA will examine whether any condition by time interaction effects exist. Post-hoc within-group analysis will be performed using paired t-tests to compare values between time-

points. Between group analyses will be performed using independent t-tests to determine if there were significant differences between the firefighter and civilian test groups at each time-point. Pearson correlation will determine if there are relationships between variables, which will be further examined by linear regression analysis.

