It is not known whether an exercise and diet intervention can reduce the blood pressure surge that occurs when a pager alarm sounds. ABP monitoring is an at home BP monitoring system, which has recently been clinically recommended by guidelines. Normal morning BP surge is established as a physiological event, yet an exaggerated surge is a known cardiovascular risk. Therefore it can be assumed that the BP surge that occurs with pager alarms must also present severe risk. In prior studies, we have found that the BP surge with pager alarm in firefighters can be extreme.

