#### ***Blood Pressure Monitoring appointment:***

This requires a visit to learn about the ambulatory blood pressure monitor and to get set-up with a cuff and monitor. The total time for this is about 30 minutes. ***This will occur on UNH campus in NH hall.*** The system is an at-home blood pressure monitor that is about the size of a cell phone. It will take measurements every half hour during a 12-hour period. While wearing the cuff and monitor, when the pager goes off, they will push the monitor's button to force an automatic blood pressure reading. We will show you how to do this during the visit to the lab. If they are a firefighter, we also ask that they remove the monitor device right before donning fire gear and take the monitor to the call on the apparatus. We ask them to remove it while wearing your gear because monitors will not record blood pressure when you move. This method is effective and has been done in the lab during our studies. This method has also been done in prior cohorts of this study that were completed at other institutions. Once they get back on the apparatus to return to station, we ask them to put the monitor back on and take another manual reading on the way back to station. After that, blood pressure measures will continue to be taken automatically at 30-min intervals.

If they are not a firefighter, we will instruct how to download a mobile app which we will use to randomly page them 1 or 2 times over the 12-hour period. They will also push the monitor's button to force an automatic blood pressure reading.

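### The test of whether the change in BP surge differs between firefighters and civilians pools the variance across two groups with different alarm stimuli; a Welch test on change scores would keep its error rate correct at almost no cost.

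*Combined protocol and SAP*

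**What the plan says.** The RESEARCH PROTOCOL section describes the design: "This study is a pre-post exercise and diet intervention study with 2 groups: firefighters and civilians". Under Post-Intervention Testing Visits, "They will complete the exact same tests after the intervention as they did before", so each outcome has two time-points.

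The DATA section gives the analysis in SPSS. It states an interest in estimating the effect on the change in surge and in whether that effect differs between groups. For this, "Repeated measures ANOVA will examine whether any condition by time interaction effects exist". All participants receive the same intervention, so I read condition as firefighter versus civilian. Paired t-tests follow within each group, and "Between group analyses will be performed using independent t-tests" at each time-point. The only distributional check named is a Shapiro-Wilk test of normality.

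The stimulus differs by group (Blood Pressure Monitoring appointment). For everyone, "when the pager goes off, they will push the monitor's button to force an automatic blood pressure reading". For firefighters the pager carries real calls, and no number per 12 hours is set. Civilians install "a mobile app which we will use to randomly page them 1 or 2 times over the 12-hour period". The only remark on the surge itself, in the INTRODUCTION, is that "we have found that the BP surge with pager alarm in firefighters can be extreme".

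**The concern.** A repeated measures ANOVA with two groups and two time-points uses one common variance for the pre-post change. If that variance differs between groups, and the groups also differ in size, the standard error of the between-group difference in change is wrong. It is too small when the smaller group is the more variable, so false differences are declared too often. It is too large when the larger group is the more variable, so real differences are missed.

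This is the test that answers the first aim. The two groups are recruited separately and reach their surge readings by different routes, so a common change variance cannot be taken for granted, and the DATA section provides neither a check nor an alternative.

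**Working it through.** **Inputs from the plan.** Two groups (RESEARCH PROTOCOL); two time-points (Post-Intervention Testing Visits); repeated measures ANOVA for the interaction (DATA).

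**Inputs assumed, because the supplied text does not give them.** Two-sided 5% level; normal change scores; no true difference; group sizes as shown; ratio of the SDs of change 1, 1.25, 1.5 or 2. The plan states no sample size, power or SD, so it has no figure to reproduce.

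**Step 1: what the interaction test is.** With individual changes d = post − pre, the interaction F is t², where

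t = (d̄₁ − d̄₂) / √[s²ₚ(1/n₁ + 1/n₂)], and s²ₚ is the pooled variance of d.

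A numerical check on one simulated data set (20 and 10 participants) gave 0.000128897 for both F and t².

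**Step 2: large-sample error rate.** Let group 1 have SD of change r and group 2 have SD 1.

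- True variance of the difference: V = r²/n₁ + 1/n₂
- Variance that the pooled test works with: P = [(n₁r² + n₂)/(n₁ + n₂)] × (1/n₁ + 1/n₂)
- Error rate: 2[1 − Φ(1.96√(P/V))]

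Smaller group more variable (n₁ = 20, n₂ = 40, r = 2): V = 4/20 + 1/40 = 0.225. P = (80 + 40)/60 × 0.075 = 0.150. 1.96 × √(0.150/0.225) = 1.60, so the error rate is 11.0%.

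Larger group more variable (n₁ = 40, n₂ = 20, r = 2): V = 4/40 + 1/20 = 0.150. P = (160 + 20)/60 × 0.075 = 0.225. 1.96 × √1.5 = 2.40, so the error rate is 1.6%.

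If r = 1, P = V at any sizes. If n₁ = n₂ = n, P = (r² + 1)/n = V for any r. Both conditions must therefore fail before the error rate moves materially. P/V depends on the sizes only through their ratio, so a larger trial with the same imbalance is no better off.

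**Step 3: simulation, 100,000 replicates per cell.** Error rate of the pooled test:

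| n, group with SD r / other group | r = 1 | r = 1.25 | r = 1.5 | r = 2 |
|---|---|---|---|---|
| 20 / 40 | 5.1% | 7.0% | 8.5% | 11.1% |
| 40 / 20 | 5.0% | 3.5% | 2.6% | 1.8% |
| 20 / 20 | 5.0% | 4.9% | 5.1% | 5.3% |
| 22 / 18 | 5.0% | 4.4% | 4.2% | 4.0% |

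Welch's test on the same changes stayed between 4.8% and 5.2% in every cell.

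**Step 4: power.** Take 40/20, with the larger group twice as variable, and a true difference at which Welch has about 79% power. In the large-sample approximation that difference is 1.96 + 0.81 = 2.77 standard errors. The pooled test needs 2.40, so its power is Φ(2.77 − 2.40) = Φ(0.37), about 64%. When variances are equal, simulated power was 78.2% for Welch and 78.9% for the pooled test.

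**Step 5: can the change variances differ?** Stable differences between people in the size of their surge cancel in post minus pre. Alarm-to-alarm variation does not cancel, because the pre and post alarms are different events. If readings were averaged over k alarms (my assumption), the noise variance would scale as 1/k, and one alarm against two would give a noise SD ratio of √2 = 1.41. Varied real calls could make firefighters the noisier group. Several calls per firefighter against a single page could make civilians the noisier group. The documents support a possible difference without a direction.

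**The case against.** The strongest reply is that no defect is shown, since every input that produces a distorted error rate is assumed. Much of this stands, and it rules out several stronger readings.

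- *That the groups will have different spread.* No SD is given for either group. The remark about extreme surges concerns size, covers firefighters only, and says nothing of the SD of a change.
- *That the error rate is wrong whenever group sizes differ.* With equal change variances the test is correct at any allocation, and at 22/18 it is only mildly conservative.
- *That firefighters are the more variable group, so the test is known to be too liberal or too strict.* The stimulus description allows either direction.
- *That the plan omits group sizes.* Part of the document was removed before review. All that can be said is that the supplied text gives none.
- *That the between-group t-tests are pooled.* The plan says only that they are independent t-tests, and SPSS supplies the unequal-variance result.
- *That the precision of a change cannot be recovered from the planned output.* The within-group paired t-tests allow it: mean change divided by t is its standard error, provided that t (non-zero) or an exact p-value is reported. Asking for confidence intervals is a reporting improvement and does not repair a loss of information.

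The argument from the stimulus also reaches only the surge. The outcomes of the second aim involve no pager, and nothing here suggests unequal variances for them.

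What the reply does not remove is that the planned test is valid only under a condition that the design gives no reason to rely on, while a test that does not need it uses the same data.

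**Conclusion.** The point holds as a conditional weakness of the interaction test for the change in BP surge. The pooling of variances follows from the design and the named method. Unequal change variances are plausible and undocumented; unequal group sizes are possible and unknown.

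The size depends on assumptions. At 2:1 sizes and SD ratios of 1.25 to 2, a nominal 5% test runs at about 7% to 11% in one direction and about 3.5% to 1.8% in the other. It stays near 5% if either the sizes or the change variances are equal. The documents do not allow a choice among these cases, so the figures show what could happen and do not estimate this trial's error rate. The change is worth making because it is cheap and protects in both directions.

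**What to change.** In the DATA section, for the change in BP surge:

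1. Replace the interaction F-test with a Welch t-test on individual change scores (post minus pre).
2. Report the difference in mean change with its Welch 95% confidence interval, and each group's mean change with its 95% confidence interval.
3. State that the between-group independent t-tests use the unequal-variance form.

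This takes a few sentences, uses data already being collected and runs in SPSS. It should be settled before outcome data are seen. The cost is a trivial loss of degrees of freedom if the variances are in fact equal (under one percentage point of power in the case above).

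The change corrects the error rate only. Real calls and app pages remain confounded with group, so even a correctly sized test compares group and alarm type together.
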